### Aims & Hypotheses:

**Aim 1:** To determine the impact of increased frequency and intensity of PT services compared to the usual care PT on discharge disposition of patients post-stroke.

**Hypothesis 1:** We hypothesize that patients receiving an increased frequency of PT services will have higher rate of discharging to home/acute rehabilitation center than to a subacute rehabilitation/skilled nursing facility compared to patients in the usual care PT group.

**Aim 2:** To determine the impact of increased frequency and intensity of PT services, as opposed to usual care, on functional mobility.

**Hypothesis 2:** We hypothesize that patients in the treatment physical therapy group will demonstrate higher degree of improvement on the Activity Measure for Post Acute Care (AMPAC) and Postural Assessment Stroke Scale (PASS) from admission to time of discharge from the hospital and at 90-day follow up. We also expect lower overall Modified Rankin Scale (mRS) scores for the increased frequency PT group compared the usual care PT group at three months post stroke.

**Aim 3:** To ensure that high frequency dosage is safe and feasible to implement the proposed PT regimen in the acute inpatient setting.

**Hypothesis 3:** We hypothesize that there will be fewer adverse events experienced by patients in the increased frequency compared to the usual care group.

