Rather than decreasing the time to upright mobility, it may be beneficial to examine the effect of short sessions of more frequent challenging mobilization in these patients, within the early stages of their hospitalization. If, as assumed, a prolonged duration of upright sitting posture has a negative effect on cerebral blood flow it may be possible to gain the positive effects of early mobility by continuing to provide PT services while combating the negative effects of cerebral perfusion by returning all patients to a supine position in bed following therapy services within the first 24 hours of acute stroke. This study aims to examine the approach of increased frequency and intensity of physical therapy services as a way to gain the benefits of the publicized early mobility approach, while weighing the concerns raised by previous trials and decreasing amount of time left upright to combat negative effects of cerebral perfusion on the ischemic penumbra. As part of this study, there will be an experimental group of participants who will receive PT sessions twice a day for the first three out of five days of admission, followed by daily treatment sessions at an intensity of at least 20-50-minute sessions. The intensity of the treatment provided to the

treatment group will be increased by incorporating error augmentation training. Error augmentation/amplification is an approach to increasing the intensity and complexity of the task without changing the task itself- thus, allowing the treatment group to participate in the same protocol of bed mobility, transfers and gait training as the control group- except with amplification of their errors rather than correction of these errors. This group will be compared to a group of control participants who will receive standard PT services 3-5x/wk (on average 20-50 minutes/session) while in the acute hospital setting.

Outcomes of interest include average length of stay, discharge disposition, Postural Assessment Stroke Scale & Modified Rankin Scale scores, and rate of readmission at 30 days. There is a critical need to evaluate how the mobilization approach of patients with acute stroke during their hospitalization impacts their discharge disposition, length of stay, and future functional outcomes

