#### **7.0 Setting**

This research will be conducted on the inpatient stroke service at MUSC (ED, 9E, 9W, 8W, ICU) within 24 hours of the patient's admission to the vascular neurology service for an acute stroke. Follow up values will be collected at post discharge neurology clinic (either in person or through password protected zoom call) by a member of the study team. Adverse events will be documented in the patient's medical chart and research record and the primary investigator will direct and oversee services provided. No additional safety risks are anticipated, other than those noted below (section 13.0)

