## **10.0 Study Design:**

This study will be designed as a randomized control trial with a 1:1 randomization. This study will utilize a permuted block design to randomly allocate a participant to a treatment group, while maintaining a balance across treatment groups. All patients will be identified and consented within 24 hours of admission.

The treatment group will receive increased frequency of PT services within the first 3-5 days of admission, followed by daily PT services for the duration of their inpatient stay. As part of the increased intensity of the treatment provided- this group will receive error augmentation training where the treating therapist will induce errors throughout mobility to challenge the patients rather than facilitating error-free movement. The deficits identified on evaluation will be targeted and emphasized throughout all therapy sessions. For patients with hemiparesis, the hemiparetic limb will be resisted during mobility. For patients with balance impairments- balance will be challenged by narrowing the base of support and resisting midline positioning

toward the side of the balance impairment. The treatment as usual group will receive standard care of PT services 3-5 times per week during their hospitalization which focuses on performing bed mobility, transfers and ambulation vs wheelchair mobility as able. Safety will be ensured throughout therapy sessions. Fall risk will be avoided with the use of a gait belt and non-skid socks and cerebral perfusion concerns will be mitigated by checking a resting blood pressure prior to upright mobility. The Postural Assessment Stroke Scale will be obtained as part of the initial PT clinical evaluation, on day three of hospital admission and at 90 day follow up. Follow up will be conducted (at 90 days +/- 15 days) via neurology clinic- either in person, through virtual clinic or, patient will be contacted via password protected Zoom. NIHSS and MRS scores will also be obtained from patient's chart on admission and at 90 day follow up. All of this data will be collected prospectively for both groups for this research study.

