## **11.0 Data Management:**

Paper consent will be stored in a locked cabinet in the PT department. All data management will be conducted using the Redcap platform developed and housed at MUSC. All other collected data will be stored electronically in the MUSC OCIO approved secure SharePoint system. Access to this database will be restricted based on netID permissions to a secured server and will only be accessible to IRB study personnel. Identifying information will be removed from the primary database. Identifying information will be stored in a separate file with a unique identifier assigned to the patient to link the two datasets.

Since this study includes only the addition of one physical therapy session a day at an

increased intensity to patients post stroke for 150 patients, it is a rather low risk study. Therefore, our data and safety monitoring plan will be continuous, close monitoring by the study investigator/co-investigators of all participants. The PI and Co-I's will meet every 25 patients to discuss data and safety monitoring. During these meetings we will look for any negative trends in the data we have collected (vitals, NIH stroke scale- ie stroke severity, and functional mobility scores) that could indicate adverse events and provide a timely summary report of adverse events to the IRB/NIH.

Any reportable safety events that are unexpected, serious or may be related to the subjects' participation in this research will be reported to the MUSC IRB in accordance with their policies.

Once the Principal Investigator (PI) determines that an adverse event meets the IRBs' reporting requirements, she will report the SAE, and related safety information, to the IRB. Supporting documents, including a copy of the Informed Consent (IC), will also be attached. For reasons of confidentiality, subjects' names will not be included in the report. If the adverse event results in the need to revise the informed consent, or other study documents, the PI will submit a study amendment to the IRB. Any trend in a type of adverse event will be relayed to the IRB as soon as the trend is noted. All events that do not meet the criteria of significant or trending, will be recorded in a summary form and included at the close of the study. Per consistency with the NIH guidelines- all serious and significant adverse events involving risks to a participant or suspension/termination of IRB approval for this study will be immediately reported to the sponsor.

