## **13.0 Risks to Subjects:**

Early mobilization in the acute stroke population may pose risks including but not limited to falls, decreased cerebral perfusion, worsening weakness and/or worsening stroke. The research team will monitor blood pressures before each PT session to make sure it is safe for the individual to participate. A confidentiality breach is also a risk associated with this research. However, no paper records will be stored or reviewed other than consent forms and only coded data will be used for the analysis. Identifying information will be removed from the primary database. Identifying information will be stored in a separate file with a unique identifier assigned to the patient to link the two datasets.

The treatment you receive may prove to be less effective or to have more side effects than the other study treatment(s) or other available treatments. The experimental treatments may have unknown side effects. The researchers will let you know if they learn anything during the course of the study that might make you change your mind about participating in the study.

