## **14.0 Potential benefits to subjects or others:**

The potential benefit to patient's is that the treatment they receive may prove to be more effective than the other study treatment or than other available treatments, although this cannot be guaranteed. This treatment may increase a patient's independence and may lead to a shorter hospital length of stay and improved functional mobility outcomes (ie: regaining the ability to stand and walk).

It is hoped that the information gained from the study will help in the treatment of future patients with similar conditions and that it will help the researcher learn more about physical therapy approach to mobility post stroke

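### Hypothesis 3 compares adverse events between arms without a common at-risk window, so the comparison can mix risk with observation

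*Combined protocol and SAP*

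**What the plan says.** Aim 3 concerns safety and feasibility. Its one hypothesis is a directional comparison between arms: "We hypothesize that there will be fewer adverse events experienced by patients in the increased frequency compared to the usual care group".

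On how events are found, section 7.0 says "Adverse events will be documented in the patient's medical chart and research record", with no schedule for asking about them. Section 13.0 says "The research team will monitor blood pressures before each PT session"; section 10.0 has a similar check before the patient is brought upright. Section 11.0 describes ongoing oversight by the investigators and a meeting after every 25 patients, at which they look for "negative trends in the data we have collected (vitals, NIH stroke scale- ie stroke severity, and functional mobility scores) that could indicate adverse events".

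On exposure, section 3.0 gives the experimental arm "PT sessions twice a day for the first three out of five days of admission, followed by daily treatment sessions", and section 10.0 gives it "increased frequency of PT services within the first 3-5 days of admission, followed by daily PT services for the duration of their inpatient stay". Section 11.0 describes the difference as one added session a day. The comparator is "control participants who will receive standard PT services 3-5x/wk (on average 20-50 minutes/session) while in the acute hospital setting". Section 14.0 says the treatment "may lead to a shorter hospital length of stay", and length of stay is an endpoint in section 4.0.

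On the end of observation, the 90-day contact collects PASS and AMPAC (section 4.0) and PASS, NIHSS and mRS (section 10.0). No adverse-event inquiry is listed. Section 12.0 withdraws patients who deteriorate, become too unstable to progress, or go to the ICU.

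**The concern.** Randomisation makes the arms comparable at baseline. It does not equalise how long, or how often, patients are observed afterwards, and here both may depend on the assigned treatment.

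Three features of the plan matter:

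- **Days observed.** If events come mainly from the inpatient chart, a shorter stay leaves fewer days on which one can be recorded.
- **Number of looks.** More sessions mean more pre-session blood pressures, and vital signs are among the data screened for possible adverse events.
- **Withdrawal.** A patient who worsens or goes to the ICU leaves the study, so recording may stop at the events a safety comparison most needs.

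The first tends to lower the experimental arm's count and the second to raise it. The third can act either way. Hypothesis 3 could thus appear supported or refuted with no true difference in risk. Section 3.0 itself reports concern about worse outcomes, mortality and falls with very early mobilisation, so Aim 3 needs an interpretable answer. Follow-up that was never collected cannot be recovered at analysis.

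**Working it through.** The plan gives no figure for adverse events. Its margin of error and power concern PASS only, so there is no stated number to reproduce here.

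**Step 1. What the comparison would rest on.**

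- Event definition: none. Section 4.0 omits adverse events, and the data list in section 10.0 has only complications.
- At-risk window: none stated.
- Unit (patients with an event, events, or rate): none stated.
- Collection after discharge: 30-day readmission is an endpoint, but no 30-day contact is described and the 90-day contact has no event question.
- Collection after withdrawal: not addressed.
- Model: section 11.0 applies a linear mixed model to all outcomes, then a logistic version for dichotomised ones. No rate model or allowance for time at risk appears.

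**Step 2. How far session counts differ.** Reading section 3.0 as two sessions on each of three days and one a day afterwards, a stay of L days (L at least 3) has 6 + (L − 3) experimental sessions. Control sessions pro rata are 3L/7 to 5L/7.

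| Stay (days) | Experimental | Control | Ratio |
|---|---|---|---|
| 3 | 6 | 1.29–2.14 | 2.8–4.7 |
| 5 | 8 | 2.14–3.57 | 2.2–3.7 |
| 7 | 10 | 3–5 | 2.0–3.3 |
| 10 | 13 | 4.29–7.14 | 1.8–3.0 |
| 14 | 17 | 6–10 | 1.7–2.8 |

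Other readings change the ratio:

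- Control patients seen on each of five days: 8/5 = 1.6.
- Section 10.0 read as two sessions a day for five days, 7-day stay: (10 + 2)/5 to 12/3, or 2.4–4.0.
- Section 11.0 read as one extra session on each of seven days: (5 + 7)/5 = 2.4 to (3 + 7)/3 = 3.3.

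The experimental arm has more sessions under every reading, but the ratio runs from about 1.6 to 4.7.

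**Step 3. Illustration with no true difference.** Assume equal underlying event rates per day and per session in both arms. Let s be the share of control events seen at sessions. The expected count ratio is

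(1 − s) × (experimental days / control days) + s × (experimental sessions / control sessions).

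The assumed control patient stays 7 days with 4 sessions.

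- Stay two days shorter, s = 0: 5/7 = 0.71.
- Equal stay, s = 0.25: 0.75 + 0.25 × 10/4 = 1.38.
- Both: 0.75 × 5/7 + 0.25 × 8/4 = 1.04.
- Equal stay, s = 0.5: 0.5 + 0.5 × 10/4 = 1.75.
- Stay two days shorter, s = 0.5: 0.5 × 5/7 + 0.5 × 8/4 = 1.36.

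**Step 4. Could a distortion of this size mislead?** Take 75 patients per arm, Poisson counts and an assumed 0.5 events per control patient. Expected counts are 75 × 0.5 = 37.5 and 37.5 × 0.71 = 26.6. Then z = |ln 0.71| / √(1/37.5 + 1/26.6) = 1.35, which gives about a 27% chance of a two-sided 5% result. The chance is 18% at 0.3 events per patient and 48% at 1.0.

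Length of stay, the reduction in stay, s and the event rates are all assumptions; the documents give none of them.

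**The case against.** A reader might infer that adverse events are found only at therapy sessions, so that looks equal sessions. The documents do not support this. Detection at sessions is an inference from the pre-session blood pressure and the screening of vital signs; the check decides whether a session is safe to start, and no section makes a low reading an adverse event. NIHSS and PASS have schedules common to both arms, investigators monitor throughout, and a fall or worsening stroke in an inpatient needs no therapy visit to be noticed. Nor is a shorter stay a stated expectation: section 14.0 offers it as a possibility after saying that benefit is not guaranteed, and no hypothesis predicts it.

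The sizes can also be challenged. Repeat blood pressures in one patient are correlated, daily risk need not be constant, and the plan places its perfusion concern in the first 24 hours, so days lost late in the stay may cost few events. The combined illustration is close to 1. All this stands, and it rules out any claim of known size or direction.

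Two further points bear on the remedy. Harm caused by extra sessions is a genuine effect of the assigned dose, so moving session events into a rate per session could hide what Aim 3 asks about; this stands. Aim 3 also refers to the acute inpatient setting, so a longer window broadens the question. But a window from randomisation includes the stay, and in-hospital events can still be shown separately.

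The intention-to-treat statement and multiple imputation in section 11.0 do not close the gap. Intention to treat needs follow-up data, and missing at random is hard to defend when observation stops because the patient worsened.

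**Conclusion.** The point holds as a design gap. Hypothesis 3 is a between-arm adverse-event comparison with no common window, no listed event inquiry at the 90-day contact and no stated follow-up after withdrawal for worsening or ICU transfer. Session counts differ by design and stay may differ, so a raw comparison can mix risk with observation.

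The documents determine neither the net direction nor the size. Ratios from 0.71 to 1.75 in the illustrations show only that a material distortion is possible under assumed stays, session counts and detection shares; 1.04 shows that the effects may nearly cancel. Nothing in the plan ensures that they do. The conclusion rests on the absence of a common window and of continued follow-up, not on any one of these numbers.

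**What to change.** Make the main Hypothesis 3 comparison the proportion of all randomised patients with at least one prespecified event: a fall, neurological worsening, ICU transfer, death or readmission. Count events over one fixed window from randomisation, the same for every patient. Thirty days would match the readmission endpoint; 90 days is the alternative, but the contact may fall at 90 − 15 = 75 days, so that window would need a rule for early contacts. Show each component by arm.

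Continue event follow-up after discharge and, where consent allows, after withdrawal under section 12.0. Ask about events in the same way in both arms at the existing 90-day contact.

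Keep falls and other listed events that occur during sessions in the arm comparison. Report pre-session blood-pressure findings separately and descriptively.

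Sections 3.0, 10.0 and 11.0 describe the experimental session schedule differently and must be reconciled.

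The cost is protocol, SAP and case-report-form wording, a short question at an existing contact, and some added follow-up of withdrawn patients. No extra visit is needed. The main downside is that events outside this hospital will rely on patient report.

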## 2.0 Background

The Department of Physical Therapy in conjunction with the Comprehensive Stroke Center at the Medical University of South Carolina (MUSC) seeks support for developing an evidence-based approach for the mobilization of patients within the first 24 hours after an acute stroke admission and for increasing the frequency of acute PT services while inpatient. This evidence will prepare physical therapists and guide the practice in the delivery of acute stroke mobilization in the hospital setting to optimize length of stay, disposition planning, and enhance long term recovery outcomes.

Very little is known about the optimal approach for mobilizing patients after an acute stroke, however, prior studies demonstrate the significance of early postural control and balance to be a prognostic indicator of a return to independent walking. Patients who do not regain sitting balance or motor recruitment strategies demonstrate an increased correlation with dependent gait at 6 weeks post stroke. Acute stroke patients may not be able to tolerate an extensive early mobility program, but may benefit from shorter more frequent sessions of

therapy early in their recovery. Therapy would focus on specific functional treatments such as seated postural control, motor recruitment strategies, and transfer training siloed into separate sessions. Throughout the literature, there is guidance for the approach to post stroke recovery in both the inpatient rehabilitation and outpatient therapy sectors. Little is known regarding the importance of frequency within the first 24 hours after an acute stroke and the contribution of therapy services in the acute hospital setting. The goal of this project is to determine the appropriate dosage of post stroke mobility in the acute care hospital setting.

The dosage of an overall treatment session is defined by the frequency, intensity and duration of physical therapy services. The objective is to determine if changing one component of the overall mobility dosage, adjusting frequency, will improve patient outcomes. As a comprehensive stroke center, MUSC strives to provide the best of patient care by committing to a higher standard of clinical service, providing a framework to improve patient outcomes, and organizing teams within the continuum of care- therapy included. A cohesive approach to mobilization in the hyper acute phase of stroke may impact patient outcomes across the continuum of care

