## 1.0 Objectives/Specific Aims

**Objective:** To evaluate the impact of increased frequency and intensity of Physical Therapy (PT) services on patient outcomes in the acute stroke population

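### The background objective and several aims and hypotheses name frequency alone, but the experimental arm changes frequency and adds error augmentation, so only the combined package can be judged

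*Combined protocol and SAP*

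**What the plan says.** The wording differs from place to place.

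- **Formal objective (Section 1.0):** "To evaluate the impact of increased frequency and intensity of Physical Therapy (PT) services on patient outcomes in the acute stroke population".
- **Aims 1 and 2 (Aims & Hypotheses):** both name the pair. Aim 1 reads "To determine the impact of increased frequency and intensity of PT services compared to the usual care PT on discharge disposition", and Aim 2 reads "To determine the impact of increased frequency and intensity of PT services, as opposed to usual care, on functional mobility".
- **Hypothesis 1**, which belongs to Aim 1, drops intensity: "We hypothesize that patients receiving an increased frequency of PT services will have higher rate of discharging to home/acute rehabilitation center".
- **Hypothesis 2** uses two labels. The sentence on AMPAC and PASS refers to the treatment group without naming a component. The sentence on mRS calls the same arm the increased-frequency group.
- **Aim 3 and Hypothesis 3 (safety and feasibility)** describe the intervention by its frequency.
- **Section 2.0 Background** lists frequency, intensity and duration as the parts of dosage, then says: "The objective is to determine if changing one component of the overall mobility dosage, adjusting frequency, will improve patient outcomes".
- **Section 3.0** again states the aim as frequency and intensity together. It describes both more sessions and a change of method for the experimental group, with errors amplified instead of corrected.
- **Section 10.0 Study Design** sets up two groups randomized 1:1. The treatment group has more sessions, and in addition "this group will receive error augmentation training". The control group has standard PT 3-5 times per week.

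**The concern.** By the protocol's own definition of dosage, the arms differ in at least two components, while Section 2.0 says that one is changed. If the report follows the frequency-only statements, it will attribute to session count a result that may come from the training method, or from the two together.

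This matters most for safety. Aim 3 and Hypothesis 3 tie the adverse-event result to frequency. Yet error augmentation, as Section 10.0 describes it, means provoking errors, resisting the weak limb and making balance harder, and Section 13.0 lists falls among the risks. Either component could produce an excess of events, and a reassuring result could not be assigned to one of them either.

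Section 2.0 also says that the evidence is meant to guide practice. A reader given a conclusion about frequency might add sessions without error augmentation, which is a regimen that this trial does not test.

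**Working it through.** **1. Which statements fit the design**

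| Statement | Names | Fits the two arms? |
|---|---|---|
| Formal objective, Section 1.0 | frequency and intensity | yes |
| Aims 1 and 2 | frequency and intensity | yes |
| Aim sentence in Section 3.0 | frequency and intensity | yes |
| Hypothesis 2, PASS/AMPAC | treatment group | yes |
| Objective sentence, Section 2.0 | frequency, as the one component changed | no |
| Hypothesis 1 | frequency | no |
| Hypothesis 2, mRS | frequency | no |
| Aim 3 | frequency | no |
| Hypothesis 3 | frequency | no |

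**2. What the contrast estimates**

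Let F be the effect of more sessions alone, E the effect of error augmentation alone, and I their interaction. The control arm has neither component and the experimental arm has both. So:

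expected difference = F + E + I

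This is one equation in three unknowns. A true difference of 2.7 PASS points is consistent with F = 2.7 and E + I = 0, with F = 0 and E + I = 2.7, or with any other split. More participants sharpen the estimate of the sum and say nothing about the split. The analysis plan in Section 11.0 compares the two randomized groups and has no step that could separate the components.

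**3. Does the wording affect the sample size?**

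Inputs from Sections 6.0 and 11.0: 75 per group, difference 2.7, 5% level, 4 time points, autoregressive correlation 0.6, power above 80%, margin of error 2.3. The plan does not say whether the test is two-sided; two-sided is assumed. The SD is taken as 7 (Section 6.0). The odd SD values in Section 11.0 look like a 7 followed by a reference number, so 7.2 is run as a sensitivity value.

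- Margin of error at one time point: 1.96 × 7 × √(2/75) = 2.24, or 2.26 with the t quantile. With SD 7.2 it is 2.30 or 2.32. The stated 2.3 is reproduced within rounding, except that 2.24 rounds to 2.2.
- Variance factor for the mean of four visits: [4 + 2(3 × 0.6 + 2 × 0.36 + 0.216)]/16 = 9.472/16 = 0.592.
- Standard error of the difference: 7 × √0.592 × √(2/75) = 0.880.
- Power: Φ(2.7/0.880 − 1.96) = 86.6%. With SD 7.2 it is 84.7%. Both agree with the stated power above 80%.

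These figures belong to the package-versus-usual-care contrast, the only one available. Rewording the objective and hypotheses leaves them as they are.

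**4. What isolating frequency would take (illustration only)**

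This uses the same model and assumes that frequency alone is worth 2.7 points. Figures are per pairwise contrast.

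| Design with a third, frequency-only arm | SD 7 | SD 7.2 |
|---|---|---|
| 50 per arm (N = 150) | 70.8% | 68.3% |
| 75 per arm (N = 225) | 86.6% | 84.7% |
| 75 per arm, frequency worth half (1.35, assumed) | 33.5% | 32.0% |

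Separating the components would be a different and larger trial.

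**The case against.** The strongest reply is that frequency is only a short label for the arm. Consecutive sentences of Hypothesis 2 use the treatment label and the frequency label for the same group. Hypothesis 1 sits under an aim that names both components, and Aim 3 also refers to the proposed regimen as a whole. Sections 3.0 and 10.0 describe error augmentation openly, and Section 11.0 mentions the added session's increased intensity. A two-arm test of a combined intervention is a legitimate design, and no frequency-only contrast is planned.

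Much of this stands. A reader might infer that the objective and all the hypotheses credit frequency alone. The documents do not support that: the formal objective, Aims 1 and 2, Section 3.0 and the PASS/AMPAC sentence do not, and Section 11.0 names PASS as the primary outcome. A reader might also infer that the trial cannot support the conclusion it was set up to draw. That too goes beyond the documents, because randomization supports a conclusion about the package. Nor does anything in the documents suggest that the two components work against each other; that is only an algebraic possibility.

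The label argument does not rescue Section 2.0. That sentence comes directly after intensity has been listed as a separate component, and it says that one component is changed. Nor does it fully cover Aim 3 and Hypothesis 3, where no paired aim supplies the missing word intensity.

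**Conclusion.** The protocol is internally inconsistent about what is being tested. Five statements (the objective sentence in Section 2.0, Hypothesis 1, the mRS part of Hypothesis 2, Aim 3 and Hypothesis 3) cannot be supported as worded, because frequency and error augmentation are completely confounded in the two arms. The safety statements are the most consequential of these. The effect of the package against usual care remains estimable, including on PASS, with the planned numbers.

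The identifiability conclusion rests only on the description of the arms and holds at any sample size. The power figures rest on an SD of 7 to 7.2, a two-sided test and the mean of four visits. They serve only to show that the correction leaves the sample-size calculation alone.

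**What to change.** Make the following edits.

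1. In Section 2.0, replace the one-component objective with the formal objective of Section 1.0.
2. In Hypothesis 1, the mRS sentence of Hypothesis 2, Aim 3 and Hypothesis 3, name the intervention as increased frequency plus error-augmentation training versus usual care. The PASS/AMPAC sentence of Hypothesis 2 needs no change.
3. Add one sentence to the analysis text in Section 11.0: the trial estimates the effect of the combined package, and no efficacy or safety conclusion will be drawn about frequency or intensity alone.

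The cost is a protocol wording amendment and a narrower claim. Arms, visits, procedures, N and power stay as planned. If the investigators do want a conclusion about frequency by itself, that needs another design, and no rewording of this one would provide it.
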